I understand the protocol and will work according to it, the principles of Good Clinical Practice [GCP; current International Council for Harmonisation (ICH) guidelines], and the Declaration of Helsinki (1964) including all amendments up to and including the October 2013 revision.

[name].
Principal Investigator
Orange County Research Center

Signature

Date

INVESTIGATOR SIGNATURE PAGE

I have read the attached protocol and agree that it contains all the necessary details for performing the study.

I will provide copies of the protocol and of the Investigator's Brochure (IB), which was furnished to me by the Sponsor, to all members of the study team responsible to me who participate in the study. I will discuss this material with them to assure that they are fully informed regarding the study treatment, including the potential risks and side effects, and the conduct of the study.

Once the protocol has been approved by the Institutional Review Board (IRB), I will not modify this protocol without obtaining the prior approval of the Sponsor and of the IRB. I will submit the protocol modifications and/or any informed consent form (ICF) modifications to the Sponsor and the IRB, and approval will be obtained before any modifications are implemented.

I understand the protocol and will work according to it, the principles of Good Clinical Practice [GCP; current International Council for Harmonisation (ICH) guidelines], and the Declaration of Helsinki (1964) including all amendments up to and including the October 2013 revision.

[name].
Principal Investigator
Orange County Research Center

Signature

Date

8/25/16

SYNOPSIS

Title	A Phase 2a, Randomized, Double-Blind, Double-Dummy, Placebo-Controlled, 3-Way Crossover Study to Compare Safety, Efficacy and Pharmacodynamics of Single and Multiple Doses of ORMD-0801 or Placebo in Adult Subjects with Type 2 Diabetes Mellitus
Indication	Type 2 Diabetes Mellitus (T2DM)
Clinical Phase	Phase 2a
Study Treatment	ORMD-0801
Dose	460 IU (16 mg) total
Dosage Regimen	Once daily, twice daily, or three times daily
Formulation	Soft gel capsules, 2 capsules per dose
Mode of Administration	Oral
Primary Objective	
 To compare pre-treatment (Day 3) to end of treatment (Day 8) 24-hour CGM glucose for single and multiple doses of ORMD-0801 vs placebo. To evaluate safety parameters for single and multiple doses of ORMD-0801 vs placebo.
Secondary Objectives	
 To compare pre-treatment (Day 3) to end of treatment (Day 8) mean daytime CGM glucose for single and multiple doses of ORMD-0801 vs placebo. To compare pre-treatment (Day 3) to end of treatment (Day 8) mean nighttime CGM glucose for single and multiple doses of ORMD-0801 vs placebo. To compare pre-treatment (Day 3) to post-treatment washout (Day 9) 24-hour CGM glucose for single and multiple doses of ORMD-0801 vs placebo. To compare post-prandial glucose measurements for single and multiple doses of ORMD-0801 vs placebo. To compare pre-treatment (Day 3) to end of treatment (Day 8) insulin pharmacokinetics (PK) for single and multiple doses of ORMD-0801 vs placebo. To compare pre-treatment (Day 3) to end of treatment (Day 8) C-peptide pharmacodynamics (PD) for single and multiple doses of ORMD-0801 vs placebo. To compare defined events of hypoglycemia for single and multiple doses of ORMD-0801 vs placebo.
Total Sample Size	Approximately 30 adult male and female subjects between the ages of 20 and 75 inclusive with T2DM.
Study Design	Following Screening, eligible subjects will enter a 3-day single-blind placebo run-in. On Day 4, each subject will be randomized to a treatment sequence that will include three treatment assignments for

	
each of three treatment Periods according to the randomization scheme. All subjects will receive placebo plus two of the following: ORMD-0801 460 IU qd, ORMD-0801 bid, or ORMD-0801 tid. Subjects will receive the randomized treatment from Day 4 through Day 8. A 24-hour single-blind placebo washout will be done on Day 9. For all treatment Periods, pre-treatment CGM data will be collected for approximately 36 hours prior to treatment (Days 1-3). The cannula will be changed and the monitor will remain in place until the morning of Day 10. Blood samples for PD analysis will be taken pre-treatment (Day 3) and at end of treatment (Day 8) to check for concentrations of insulin and C-peptide in the blood. In addition, adverse events, clinical laboratory values, vital signs, and ECGs will be evaluated periodically for safety. Subjects will be discharged on the morning of Day 10. Each treatment Period will be separated by a 2-week washout. A final follow-up visit will be performed 1 week after the end of the third treatment Period.


Summary of Assessments
	
Safety will be verified by monitoring adverse events, clinical laboratory values, vital signs, physical examinations, and ECG.
 
CGM Monitoring will be used throughout the entire treatment period to compare pre-treatment, treatment, and post-treatment glucose levels, as well as post-prandial glucose.
 
Pharmacokinetics/Pharmacodynamics will be used to compare pre-treatment and post-treatment C-peptide and insulin levels.

Duration of Participation
	
Subjects will be evaluated for participation in the study during a 7-10 day Screening period. The planned length of participation is about 65 days (from Visit 2 through Visit 3). During each Visit 2 treatment Period, the subjects will be confined to the unit for 8 nights from check-in on the evening of Day 2 through completion of the post-treatment procedures on the morning of Day 10.

Subject Selection Criteria
	
This study will enroll T2DM subjects with an HbA_{1c} $\geq 7.5\%$ and $\leq 10.5\%$, who are taking metformin only, metformin in addition to sulfonylurea, metformin in addition to TZD, metformin in addition to an SGLT-2 inhibitor, or metformin in addition to a DPP-4 inhibitor with all treatment regimens stable for a minimum of 8 weeks prior to Visit 2/Period 1/Day 1.

Statistical Methods
	
Pharmacokinetics/Pharmacodynamics (PK/PD) The PK/PD analysis will be conducted using model-independent methods and will be based on plasma concentrations of insulin and C-peptide.
 
Continuous Glucose Monitoring The placebo adjusted change in means will be analyzed using an Analysis of Variance (ANOVA) with treatment as the main effect to

	
determine whether multiple doses a day has an effect on the CGM parameters.
 
The ratios of the placebo adjusted change in means between the active treatments within each subject will also be derived to estimate the magnitude of the dose response.
 
Summary statistics will be presented for both the placebo adjusted change in means and the ratios of the placebo adjusted change in means. Analysis results will be presented for the change in means.
 
Safety All safety parameters will be summarized and listed using descriptive statistics.

--	--

Table of Contents

TITLE PAGE	1
SPONSOR PROTOCOL APPROVAL SIGNATURE PAGE	2
INVESTIGATOR SIGNATURE PAGE	3
SYNOPSIS.....	4
LIST OF ABBREVIATIONS AND DEFINITIONS OF TERMS.....	11
1 INTRODUCTION	13
2 STUDY OBJECTIVES.....	15

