3 INVESTIGATIONAL PLAN

3.1 Overall Study Design and Plan

This study will enroll approximately 30 adult subjects with T2DM from age 20 to 75 inclusive. Following a 7-10 day Screening period, eligible subjects will enter a 3-day single-blind placebo run-in. On Day 4, each subject will be randomized to a treatment sequence that will include three treatment assignments for each of three treatment Periods according to the randomization scheme. All subjects will receive placebo plus two of the following: ORMD-0801 460 IU **qd**, ORMD-0801 **bid**, or ORMD-0801 **tid**. Subjects will receive the randomized treatment from Day

4 through Day 8. A 24-hour single-blind placebo washout will be done on Day 9. For all treatment Periods, pre-treatment CGM data will be collected for approximately 36 hours prior to treatment (Days 1-3). The cannula will be changed and the monitor will remain in place throughout the 5-day treatment period (Days 4-8) and for an additional 24 hours post-treatment (Day 9). Blood samples for PD analysis will be taken pre-treatment (Day 3) and at end of treatment (Day 8) to check for concentrations of insulin and C-peptide in the blood. In addition, adverse events, clinical laboratory values, vital signs, and electrocardiograms (ECGs) will be evaluated periodically for safety. Subjects will be discharged on the morning of Day 10. Each treatment Period will be separated by a 2-week washout. A final follow-up visit will be performed 1 week after the end of the third treatment period.

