- Adverse events will be monitored and recorded.
- Subjects will be discharged for a minimum 2-week washout period.

3.3.2 Period 2

Subjects will report to the CRU on the morning of Day 1.

3.3.2.1 Day 1

- Review of medical history;
- Review of medications and supplements;
- Measurement of vital signs (weight, seated SBP/DPB, and heart rate);
- Provide the first dose of single-blind placebo at least 45 minutes prior to breakfast;
- Provide breakfast;
- Subjects will be fitted with the continuous glucose monitoring (CGM) device and data recording will begin;
- Provide 4 doses of single-blind placebo and instruct subjects to take one dose at least 45 minutes before lunch, one dose at bedtime, one dose at least 45 minutes before breakfast on Day 2, and one dose at least 45 minutes before lunch on Day 2.
- Adverse events will be monitored and recorded.
- Subjects will be instructed to return to the CRU at approximately 5pm (\pm 30 minutes) on Day 2.

3.3.2.2 Day 2

- Admission to the CRU at approximately 5pm (\pm 30 minutes);
- Review of medications and supplements;

- Measurement of vital signs (weight, seated SBP/DPB, heart rate, and temperature);
- Perform breathalyzer;
- Collect a urine sample for:
 - Drug screen;
 - Pregnancy testing (WCBP only)
- Provide a standardized diabetic meal at approximately 7pm (\pm 60 minutes). Standardized meals will continue throughout the remainder of the study Period.
- Provide a dose of single-blind placebo at approximately 10pm (\pm 60 minutes).
- Continue CGM monitoring;
- Adverse events will be monitored and recorded.

3.3.2.3 Day 3

- Review of medications and supplements;
- Measurement of vital signs (weight, seated SBP/DPB, heart and rate);
- Provide a dose of single-blind placebo at approximately 7am (\pm 60 minutes);
- Provide breakfast no sooner than 45 minutes after the morning dose;
- Provide a dose of single-blind placebo at approximately 1pm (\pm 60 minutes), at least 45 minutes prior to lunch;
- Provide lunch no sooner than 45 minutes after the afternoon dose;
- Provide dinner at approximately 7pm (\pm 60 minutes);
- Provide a dose of single-blind placebo at approximately 10pm (\pm 60 minutes);
- Collect a blood sample according to schedule (per randomization scheme, either morning, afternoon, or evening) prior to the specified dose of placebo for:
 - Pre-dose PD analysis
 - Serum chemistry

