8.3 Continuous Glucose Monitor Evaluation

For the purpose of analysis:

- 24-hour will be considered to be from 6AM to 6AM,
- Daytime will be considered to be from 6AM to 10PM, and
- Nighttime will be considered to be from 10PM to 6AM.

The last 2 days with at least 80% of expected measurements prior to dosing will be considered the run-in days for each of the parameters. The last 2 days with at least 80% of expected measurements prior to 8 hours after the last dose will be considered the on treatment days. The measurements more than 8 hours after the last dose will be considered the follow-up days.

The area under the curve (AUC) will be derived for each of the time periods (24-hour, daytime and nighttime) using the indicated days (run-in days, treatment days and follow-up days). The average glucose measurement will be derived by dividing the AUC by the number of observed hours. The average change from run-in will be derived for each treatment regimen for both the treatment days and the follow-up days.

The placebo adjusted change in means will be derived for each of the active therapy regimens by subtracting the placebo mean (the mean change from run-in while the subject was receiving placebo) from the active therapy mean (the mean change from run-in while the subject was receiving the active therapy). The placebo adjusted change in means will be derived for both the treatment days and the follow-up days.

The placebo adjusted change in means will be analyzed using an Analysis of Variance (ANOVA) with treatment as the main effect to determine whether multiple doses a day has an effect on the CGM parameters.

The ratios of the placebo adjusted change in means between the active treatments within each subject will also be derived to estimate the magnitude of the dose response.

Summary statistics will be presented for both the placebo adjusted change in means and the ratios of the placebo adjusted change in means. Analysis results will be presented for the change in means.

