2.8. Efficacy Evaluations

2.8.1. Continuous Glucose Monitoring

The last 2 days with at least 80% of expected measurements prior to dosing will be considered the run-in days for each of the parameters. The last 2 days with at least 80% of expected measurements prior to 8 hours after the last dose will be considered the on treatment days. The measurements more than 8 hours after the last dose will be considered the follow-up days.

The 24-hr period (6AM to 6AM), nighttime (from 10pm to 6am), daytime (6AM to 10PM), and post-prandial (first hour after meal start time including breakfast, lunch, and dinner) glucose values will be summarized. The mean, standard deviation, minimum, maximum, first quartile, median, third quartile and inner-quartile range will be presented.

The area under the curve (AUC) will be derived for each of the time periods (24-hour, daytime and nighttime) using the indicated days (run-in days, treatment days and follow-up days). The average glucose measurement will be derived by dividing the AUC by the number of observed hours. The average change from run-in will be derived for each treatment regimen for both the treatment days and the follow-up days.

The placebo adjusted change in means will be derived for each of the active therapy regimens by subtracting the placebo mean (the mean change from run-in while the subject was receiving placebo) from the active therapy mean (the mean change from run-in while the subject was receiving the active therapy).

The placebo adjusted change in means will be derived for both the treatment days and the follow-up days. The placebo adjusted change in means will be analyzed using an Analysis of Variance (ANOVA) with treatment as the main effect to determine whether multiple doses a day has an effect on the CGM parameters. If the residuals are not normally distributed, then a Kruskal-Wallis test (one-way analysis of variance on the ranks) will be performed.

The ratios of the placebo adjusted change in means between the active treatments within each subject will also be derived to estimate the magnitude of the dose response.

Summary statistics will be presented for both the placebo adjusted change in means and the ratios of the placebo adjusted change in means. Analysis results will be presented for the change in means.

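### The CGM analysis of this three-period crossover has no period term, so a period effect on the change from run-in would widen the intervals and, without period balance, could shift the regimen estimates

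*Protocol*

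**What the plan says.** The CGM model appears in the same words in the Protocol synopsis, Protocol 8.3 and SAP 2.8.1: "The placebo adjusted change in means will be analyzed using an Analysis of Variance (ANOVA) with treatment as the main effect". None of the three places names period, sequence or subject. The SAP's fallback for non-normal residuals is also single-factor: "then a Kruskal-Wallis test (one-way analysis of variance on the ranks) will be performed".

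The analysed value is formed by "subtracting the placebo mean (the mean change from run-in while the subject was receiving placebo) from the active therapy mean" (SAP 2.8.1). Each component is a change from a run-in inside its own period: "The average change from run-in will be derived for each treatment regimen for both the treatment days and the follow-up days" (Protocol 8.3).

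On design, the synopsis says "All subjects will receive placebo plus two of the following: ORMD-0801 460 IU qd, ORMD-0801 bid, or ORMD-0801 tid". Each subject therefore contributes two placebo-adjusted values that share one placebo change. On spacing, Protocol 3.3.1.8 says "Subjects will be discharged for a minimum 2-week washout period".

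SAP 2.12 leaves the sequences to a separate randomization plan. Protocol 8.1 and SAP 2.11 say that the study is not powered. Neither document gives an SD, effect size or alpha for CGM.

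**The concern.** Every placebo-adjusted value compares two different admissions weeks apart. If the change from run-in to treatment differs between the first, second and third admission, that difference is part of the value, and the planned model can only count it as noise or as regimen effect.

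There is a plausible route. Under Protocol 3.3.1, subjects are at home from Day 1 until about 5pm on Day 2, and standardised meals resume with dinner that evening. The run-in baseline can reach back into that time, while the treatment days are fully confined. The change from run-in therefore contains a home-to-unit transition, repeated three times, and the first need not act like the third. The documents neither show nor exclude this.

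At stake is the precision of the primary CGM estimates and, if periods are unbalanced, their location. Period is fixed by the design and known for every value.

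**Working it through.** **1. Spacing, checked against the stated length.** Day 1 to Day 10 is 9 days. Adding the 14-day minimum washout gives a 23-day cycle, so like days are 23 days apart in adjacent periods and 2 × 23 = 46 in Periods 1 and 3. Period 3 Day 10 is study day 46 + 10 = 56, and follow-up 7–9 days later is day 63–65. Counting 14 clear days gives cycles of 24 and 48 days and follow-up on day 65–67. Both agree with the synopsis figure of about 65 days. The spacings are derived minimums, not stated figures.

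**2. What cancels.** Let period k shift the glucose level by λₖ on all its days and shift the run-in-to-treatment change by πₖ. The run-in subtraction removes λₖ and the subject's own level. A placebo-adjusted value is then

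D = τ + (π_active − π_placebo) + e_active − e_placebo.

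In simulation, a level shift of 2σ per period left the residual mean square at 2.00σ², as with no shift.

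**3. What stays in the residual.** Let πₖ drift by d per period and let all six orders be equally likely. The period difference is ±d in 4 of 6 placements and ±2d in 2 of 6, so its variance is (4d² + 2·4d²)/6 = 2d². Hence Var(D) = 2σ² + 2d².

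**4. Size in mg/dL.** Assumptions: σ = 15 or 20, and 10 subjects per regimen pair, hence 20 values per regimen and 60 in all. The one-way model has 57 residual df, t about 2.00.

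| σ | d | 2σ² + 2d² | 2σ² | Width ratio | Narrower by |
|---|---|---|---|---|---|
| 15 | 5 | 500 | 450 | √(450/500) = 0.949 | 5.1% |
| 20 | 5 | 850 | 800 | √(800/850) = 0.970 | 3.0% |
| 15 | 10 | 650 | 450 | √(450/650) = 0.832 | 16.8% |
| 20 | 10 | 1000 | 800 | √(800/1000) = 0.894 | 10.6% |

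For σ = 15, d = 10 the planned width is 2 × 2.00 × √(650/20) = 22.8 mg/dL. Simulation (1,500 trials per setting, near-balanced orders, period entered as two period-difference covariates) gave:

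- d = 10: 22.7 without period against 18.7 with it at σ = 15, and 28.3 against 25.2 at σ = 20 (11–18% narrower).
- d = 5: 3–6% narrower.
- d = 2: about 1% narrower with balanced orders, a slight loss with random orders.
- Period 1 alone differing by 10–15 mg/dL: 4–14% narrower.
- No period effect: at most about 2% wider.

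**5. The estimates.** With random orders, the SD of a regimen-minus-placebo estimate in units of σ was:

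| d/σ | Treatment only | Subject + period + treatment |
|---|---|---|
| 0 | 0.310–0.318 | 0.297–0.307 |
| 0.25 | 0.320–0.333 | 0.299–0.311 |
| 0.5 | 0.353–0.365 | 0.300–0.310 |
| 1 | 0.442–0.454 | 0.304–0.311 |

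The average bias is zero. The chance imbalance has SD √(2/20)·d = 0.32d over 20 subjects. At σ = 15, d = 10, adding the period covariates cut the RMSE from 5.7 to 4.9 mg/dL.

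**6. Balance.** With 10 subjects per pair, no treatment can occupy each period equally often within a pair (10/3). What matters, though, is balance per regimen over its 20 subjects, and enumeration found an allocation that achieves it. For qd, for example, the active-minus-placebo counts over Periods 1–3 are (−1, 0, +1) in one pair and (+1, 0, −1) in the other, which sum to zero. Under that allocation the estimates were unbiased with SD 0.31–0.32σ, but at d = σ the residual mean square was still 4.1σ² and the nominal SE 0.45σ.

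**The case against.** The strongest reply is that the planned analysis gives no false claims. In simulation the coverage of its 95% intervals stayed at 94–97% in every setting: 97% with balanced orders at SD 15 and a drift of 10 mg/dL, and 95% with unbalanced orders. With balanced orders the estimate hardly changes (RMSE 4.96 against 4.79 mg/dL in that setting). Dosing times, confinement and unit meals are the same in all periods, background therapy is stable for 8 weeks before entry, and the study is declared not powered. All of this stands. The problem is lost efficiency, with a possible shift under imbalance.

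A reader might go further in three ways, and the documents do not support any of them.

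- **That any period effect contaminates the results.** A constant level shift cancels. The 23- and 46-day gaps most readily suggest slow drift in level, so they are weak evidence by themselves.
- **That 10 subjects per pair, divisible by neither 6 nor 3, proves bias.** The even split is itself an assumption, and balance per regimen is attainable. The sequence list is not available here.
- **That intervals are known to be 11–18% too wide.** This needs a drift in the change of 10 mg/dL per period, which is 0.5–0.67 of the assumed SD, and the documents give no such figure.

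Being unpowered does not remove the point. The output is then estimates and their precision, and the ANOVA is still meant to judge whether multiple daily doses have an effect.

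**Conclusion.** The point holds in limited form, as a cheap improvement. Treatment is the only named factor in a three-period crossover. A period effect on the change from run-in, if present, inflates the residual even under perfect balance. Whether it also shifts the regimen estimates depends on the allocation and on dropout (Protocol 4.3 does not replace treated subjects who withdraw), and the documents settle neither.

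The size rests on assumed values: an SD of 15–20 mg/dL for one period-level change, 10 subjects per pair and a linear drift. On these, the gain in CI width is about 3–6% at 5 mg/dL per period and 11–18% at 10, against a cost of at most about 2% with no period effect.

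**What to change.** In the synopsis, Protocol 8.3 and SAP 2.8.1, analyse the per-period change from run-in with treatment (placebo, qd, bid, tid) and period as fixed effects and subject as a blocking effect, fixed or random. Report period-adjusted regimen-minus-placebo and between-regimen differences with 95% CIs, for both treatment and follow-up days. Match the one-way rank fallback to this model, since it has no place for period or subject.

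If the placebo-adjusted variable is kept, add two covariates: the Period 2 indicator of the active period minus that of the placebo period, and the same for Period 3. Also account for the two values per subject that share one placebo change (correlation 0.5). The covariates alone do not do this: at an assumed nominal 5% level, the regimen F-test rejected about 2% of the time under the null with or without them.

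The cost is SAP wording and two degrees of freedom for period. With 90 period-level changes and fixed subject effects, 90 − (30 + 2 + 3) = 55 residual df remain, against 60 − 3 = 57 in the planned model. No new data are needed.
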